## 8.7 Reading a Case

At each site and after appropriate training, four pathologists participating at that site will read the same set of case slides, unique to each site. Each pathologist shall read each case on a conventional light microscope (Reference Method; Glass) and on the Hamamatsu system (Test Method; WSI) in an order randomly determined.

RPs will receive from the site coordinator the slides and/or WSI images to be read. The case study identification, patient age and gender, relevant supplemental clinical history, part and procedure information, and specimen gross description in the EDC system in addition to corresponding slides (either glass or WSI) will be available for RP viewing, but RP will never have access to the final sign-out diagnosis or GT information. Pathologists may not request re-scans of any slide. No additional slides from the case can be requested. Reading Pathologists will not be permitted to order additional re-cuts or stains outside of what was cut/stained during the original clinical review process (i.e., no additional slides will be created for the purpose of this study) and selected by the EP and VEP.

All RPs will perform randomized (read-order) glass and WSI reads with a minimum 4-week washout period between modalities. The order of reading will be randomly assigned such that each case will either be read first using glass slides and LM and then (following a 4-week wash-out period) via WSI or vice versa. All digital reads will be executed using the Hamamatsu Pathology workstation. Pathologists will access the Hamamatsu system via secure login/password. For viewing by glass, the pathologist shall use the light microscope that they normally use at that site.

When the RP reads the cases, all WSI and glass diagnoses, as well as supplemental information based on truncated CAP checklists developed for this study, will be entered into an eCRF using an EDC system.

The RP will write a primary diagnosis in a narrative text in their words.

Next, the reader pathologist shall fill in an abridged CAP checklist to capture supplemental diagnostic information specific to each of the organ malignancy types in the study, if applicable. The abridged checklist will include only those items most relevant to the patient's management, i.e., type, grade, margin and whether infiltration into lymph nodes. The pathologist may use information from an abridged

CAP checklist to clarify and complete the diagnosis description that satisfies the primary diagnosis. The RP may use textbook reference materials to assist in determination of diagnosis.

The reading pathologist will be trained and given instructions how to use the CAP checklist information when writing the text that shall describe the reading pathologist's diagnosis.

**Possibility of Deferral:** Reader must do her or his best effort to determine a primary diagnosis. However if the reading pathologist feels strongly that he or she is not able to make a diagnosis, then the reader pathologist may record that in the case report form. The recording can be "deferral to Glass" in the case of WSI, or "deferral to specialist" in either case of Glass or WSI.

RPs will not be able to review eCRFs for which a diagnosis is finalized (case signed-out).

## 8.8 Adjudication of Discordant Readings

Once the RP eCRF is reviewed, queried, cleaned and completed, that reading will be sent to the adjudicators to adjudicate the endpoint.

The adjudicator pathologist (AP) is part of an independent board of subject matter expert, board certified pathologists, who shall review and compare diagnoses on WSIs and on Glass to the GT, the original diagnosis that was rendered in the clinical practice. The AP(s) shall not be presented with the slides or WSI images. The adjudicators shall be presented only with the ground truth primary diagnosis and synoptic information, the patient case notes available to the reading pathologist, and the reading pathologist primary diagnosis and supplemental CAP checklist records.

When the adjudicator is presented with a case to adjudicate, the 1st and 2nd adjudicator will independently review the case. If a disagreement involving a major discordance is present between the 2 adjudicators, such a case will go to the 3rd member to adjudicate. Based on the determination of the 3rd member, the majority choice will be selected. If there is no majority from the rulings of the 3 adjudicators, then the adjudication will proceed to a consensus meeting for final decision.

**Table 3: Definition of Discordance**

Severity	Definition
Minor	No Harm: 

Will not result in harm

No change in prognosis or a change in prognosis that is unlikely to result in a change in treatment according to standard care.

	Minimal Harm [Grade 1] 

Further unnecessary noninvasive diagnosis test(s) performed [e.g., blood tests or non-invasive radiological examination].

Delay in diagnosis or therapy of < 6 months.

Minor morbidity due to [otherwise] unnecessary further diagnostic effort(s) or therapy predicated on the presence of [unjustified] diagnosis.

Major	Moderate Harm [Grade 2]

Table 3: Definition of Discordance	
Severity	Definition
	

a. Further unnecessary invasive diagnostic test(s) [e.g., tissue biopsy, re-excision, angiogram, radionuclide study, or colonoscopy].

b. Delay in diagnosis or therapy of > 6 months.

c. Major morbidity lasting < 6 months due to [otherwise] unnecessary further diagnostic effort(s) or therapy predicated on the presence of [unjustified] diagnosis.

	
Severe Harm [Grade 3]
 

a. Loss of life or limb, or other body part, or long-lasting morbidity [lasting > 6 months].

## 8.9 Pilot Studies

Before the study starts, the sponsor may choose to conduct one or more optional pre-study mock pilot trials of certain key procedures, specifically the screening and enrollment, reader pathologist diagnosis and adjudication procedure. This pilot is an extension of the user acceptance testing and is to allow the sponsor to observe and optimize the combined operation and workflow of training, procedures and eCRF recordings to insure processes are operational as expected, and consistent amongst participants.

The pilot will include participation of the actual pathologists and scanning technicians who are assigned in the study. Each pilot may be a full or abbreviated test of the actual study procedure by those participants. Each pilot may use upwards of 5-10 de-identified cases from the archive. And, so to not interfere with the cases selection process, these pilot cases are to be selected with accession dates less than 1 year from non-active cases. In order to insure pilots are being done correctly, the sponsor and consultants may review pilot data and compare against de-identified pathology reports and scans of de-identified histochemical slides for that pilot case.

## 9. STATISTICAL CONSIDERATIONS

The statistical analysis plan (SAP) will be developed and finalized before database lock and will describe the set of data to be included in the analyses, and procedures for accounting for missing, unused, and spurious data. The SAP may also include additional exploratory analyses not explicitly mentioned in the following sections.

### 9.1 Statistical Hypotheses

The primary statistical objective of this study is to demonstrate that the safety and accuracy of the Hamamatsu system is non-inferior to the Diagnostic Reference Standard glass diagnosis in routine surgical pathology cases.

Assuming a non-inferiority margin of 4%, consistent with the literature (8-10) and with the target to which the PIPS' clearance was held, then the hypothesis to be tested can be written as:

$$H_0: \pi_{WSI} - \pi_{Glass} > 0.04 \text{ Versus } H_1: \pi_{WSI} - \pi_{Glass} \leq 0.04$$

where  $\pi_{WSI}$  and  $\pi_{Glass}$  are the major discordance rates for WSI and Glass respectively.

## 9.2 Sample Size Calculations

Assuming  $E\{d_{li}\} = \Delta$  and variance  $\text{Var}\{d_{li}\} = \sigma^2$  where  $d_{li}$  is equal to average over differences of error rates between WSI and Glass compared to GT diagnosis for case  $i$  in site  $l$ , the following expression is

$$\text{applicable: } n = \frac{(Z_\alpha + Z_\beta)^2(\sigma^2)}{(\delta + \Delta)^2} / \frac{(Z_\alpha + Z_\beta)^2 \pi'_{WSI}(1 - \pi'_{WSI}) \pi'_{Glass}(1 - \pi'_{Glass}) \{1 - \lambda + (r - 1)(\xi - \eta)\}}{r(\delta + \Delta)^2}$$

For which  $\pi'_{WSI}$  and  $\pi'_{Glass}$  are the probabilities that WSI and Glass methods agree (or minor discordance) with the GT diagnosis classification retrospectively;  $\lambda = \text{Corr}(a_{lij_1}, a_{lij_2})$ , the correlation between the classifications for the two modalities by the same reader;  $\xi = \text{Corr}(a_{lij_k}, a_{lij'_k})$ , the correlation between two readers for a given modality; and,  $\eta = \text{Corr}(a_{lij_1}, a_{lij'_2})$ , the correlation between two modalities and between two readers.

Assuming power =  $(1 - \beta) = 0.90$ ,  $\alpha = 5\%$  two-sided, a non-inferiority margin of  $\delta$ , a true difference between proportions of WSI and Glass equal to  $\Delta$  in favor of Glass, number of readers  $r = 4$  and number of sites = 4, the required sample size is provided in [Table 4](#) for different ranges of  $\pi'_{WSI}$ ,  $\Delta$ ,  $\lambda$ , and  $(\xi - \eta)$ .

Table 4: Sample Size for 4 Readers and 4 Sites								
$\pi'_{WSI}$	$\lambda$	$(\xi - \eta)$	Max $\sigma^2$ ( $\sigma^2$ for $\Delta = 0$ )	$\Delta = \pi'_{WSI} - \pi'_{Glass}$				
				0.0	-0.5%	-1.0%	-1.5%	
0.6	0.5	0.150	0.114000	749	976	1326	1904	2968
		0.125	0.105000	690	899	1221	1754	2733
		0.100	0.096000	631	822	1116	1604	2499
	0.6	0.150	0.102000	670	874	1186	1704	2655
		0.125	0.093000	611	796	1082	1553	2421
		0.100	0.084000	552	719	977	1403	2187
0.7	0.5	0.150	0.099750	665	852	1154	1653	2568
		0.125	0.091875	604	785	1063	1522	2366
		0.100	0.084000	552	718	972	1392	2163
	0.6	0.150	0.089250	587	762	1032	1479	2298
		0.125	0.081375	535	695	941	1348	2095
		0.100	0.073500	483	628	850	1218	1893
0.8	0.5	0.150	0.076000	500	646	871	1241	1920
		0.125	0.070000	460	595	802	1143	1768
		0.100	0.064000	421	544	733	1045	1616

Table 4: Sample Size for 4 Readers and 4 Sites								
$\pi'_{WSI}$	$\lambda$	$(\xi-\eta)$	Max $\sigma^2$ ( $\sigma^2$ for $\Delta = 0$ )	$\Delta = \pi'_{WSI} - \pi'_{Glass}$				
				0.0	-0.5%	-1.0%	-1.5%	-2.0%
0.6	0.150		0.068000	447	578	779	1111	1718
	0.125		0.062000	408	527	710	1013	1566
	0.100		0.056000	368	476	642	915	1414

This table shows, a total of 2000 cases will provide more than 90% power to demonstrate non-inferiority of WSI to Glass with a non-inferiority margin of 4% as long as the proportion of agreements with Ground Truth is at least 60%,  $\lambda$  is at least 0.5,  $(\xi-\eta)$  is at most 0.15, and  $\Delta \geq -1.5\%$ .

### 9.3 Populations for Analyses

**All Available Population (AAP):** AAP includes all cases for which at least one reader provides an evaluable outcome for either the WSI or Glass modality where an outcome is considered evaluable if the adjudication committee is able to classify the diagnosis as concordant, minor discordant, or major discordant with the Ground Truth diagnosis. If a reading pathologist is unable to complete study reads, a replacement pathologist may be selected by Hamamatsu, the re-reads by the replacement pathologist are supplementary, and the primary analysis will use all readings by the original/previous pathologist, with the readings by the replacement pathologist only being used for cases that the original/previous Reading Pathologist did not read by both modalities.

### 9.4 Statistical Analyses

This section is a summary of the planned statistical analyses of the primary and secondary endpoints described in detail in the study SAP.

#### 9.4.1 Case Characteristics and Disposition, and Reader Pathologists

The characteristics of the cases selected at each site and overall will be descriptively summarized using numbers and percentages. The characteristics of the cases will include, the case breakdown as specified in Table 2, including organ system, procedure type, overall classification.

The number and percentage of deferrals will be summarized by reader, site, and overall for each modality. The reason for the deferral will also be provided.

The characteristics of the reader pathologists at each site and overall will be descriptively summarized in regard to years in practice and specialty.

#### 9.4.2 Primary Analysis of Non-inferiority of WSI Relative to Glass

The AAP will be used for the primary analysis. To evaluate the major discordance rates between WSI and Glass, a mixed model repeated measures (MMRM) logistic regression will be performed. The indicator of major discordance (yes/no) will be the dependent variable with modality (WSI or glass), as a fixed effect; and site, reader and case entered into the model as random effects; glass will be the reference

group. From this model, a two-sided 95% confidence interval (CI) for the difference in major discordance rate ( $\pi_{WSI} - \pi_{Glass}$ ) will be constructed. If the upper bound of the 95% CI is less than the non-inferiority margin of 4%, then WSI will be considered non-inferior to Glass.

A summary table will provide the number of deferrals and reasons for deferral (e.g., deferral to specialist, deferral to glass, etc.). Cases with diagnosis deferred for at least one modality (excluding missing observations) will be excluded from the primary analyses.

The point estimates and the corresponding two-sided 95% confidence intervals of the major discordance rates will be provided separately for WSI and glass. To support the clinical performance of NanoZoomer, the major discordance rate for WSI should not exceed 7%.

#### 9.4.2.1 *Sensitivity Analysis*

Sensitivity analyses will be performed to evaluate the robustness of the results. All deferred plus missing data cases will be assumed as having major discordance with GT and included in the same MMRM logistic regression analysis as that of the primary analysis.

#### 9.4.2.2 *Generalizability for Readers and Sites*

The WSI vs. glass difference in major discordance rate and associated 95% CI by reader will be constructed using the primary MMRM logistic regression model. The 16 such confidence intervals for the 4 readers at the 4 sites will be descriptively displayed in a Forest Plot. The extent to which the respective confidence intervals in the Forest Plot are overlapping sheds light on their homogeneity, and reasonably homogeneous confidence intervals can support generalizability with respect to readers in the sense of comparability of estimated differences between WSI and Glass for the 4 readers at the 4 sites.

Generalizability for sites will be addressed in a similar way to that previously discussed for readers within sites. The 4 confidence intervals for the 4 sites can be descriptively displayed in a Forest Plot. The extent to which the respective confidence intervals in the Forest Plot are overlapping sheds light on their homogeneity, and reasonably homogeneous confidence intervals can support generalizability with respect to sites in the sense of comparability of estimated differences between WSI and glass for the 4 sites.

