#### **11.1.2 Primary Analysis of Non-inferiority of WSI Relative to Glass**

##### Primary Analysis Model

The primary analysis of the adjudicated comparison of each modality to the GT diagnosis will be performed using a repeated measures logistic regression model. In this model, the dependent variable is major discordance status, yes versus no. Modality (Glass or WSI), will be included in the model as fixed effect; and, site, reader, and case will be included as random effects. The AAP will be used for the primary analysis; however, any reading classified as “deferred” or as missing data will be excluded. The mixed model repeated measure (MMRM) logistic regression model can be written as:

$$\text{Ln} \left[ \frac{P(Y_{ilfh} = 1)}{1 - P(Y_{ilfh} = 1)} \right] = \mu + \alpha_i + s_l + r_{f(l)} + \beta_{h(l*j)} + \varepsilon_{ilfh} \quad (1)$$

where  $P(Y_{ilfh} = 1)$  is the probability that the diagnosis is discordant with GT and  $Y_{ilfh}$  is the dichotomous outcome for case  $h$  ( $h = 1, 2, \dots, 250$ ), by reader  $f$  ( $f = 1, 2, 3, 4$ ), within site  $l$  ( $l = 1, 2, 3, 4$ ) using modality  $i$  ( $i = 1, 2$ ).

$\mu$  is the overall mean.

$\alpha_i$  is a fixed effect due to modality  $i$ ;  $\sum \alpha_i = 0$

$s_l$  is a random effect due to site  $l$ ;  $s_l \sim N(0, \sigma^2_s)$ , and the  $s_l$  are independent.

$r_{f(l)}$  is a random effect due to reader  $f$  nested within site  $l$ ;  $r_{f(l)} \sim N(0, \sigma^2_r)$ , and the  $r_{f(l)}$  are independent

$\beta_{h(l)}$  is a random effect due to case  $h$  nested within site  $l$ ;  $\beta_{h(l)} \sim N(0, \sigma^2_\beta)$ , and the  $\beta_{h(l)}$  are independent.

$\varepsilon_{ilfh}$  is the random error;  $\varepsilon_{ilfh} \sim N(0, \sigma^2_\varepsilon)$ .

The random components are independent from each other.

Using model (1), the difference in major discordance rate ( $\pi_{WSI} - \pi_{Glass}$ ) will be estimated and corresponding two-sided 95% confidence interval (CI) will be derived. If the upper bound of the 95% CI is less than the non-inferiority margin of 4%, then WSI will be considered non-inferior to Glass.

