##### **11.2.1 Accuracy by Site, Reader, Organ, and Case Subtype/Procedure**

###### **11.2.1.1 Accuracy by Site**

To describe the accuracy of WSI relative to Glass by site, the MMRM logistic model (1) with the omission of the site variable will be used. For each of the four sites, the estimated major discordance rates for the two modalities, their difference ( $\pi_{WSI} - \pi_{Glass}$ ), and their corresponding two-sided 95% CIs will be presented in

tabular format. In addition, cross tabulation of the observed, unmodeled major discordance rates for the two modalities will be presented as well.

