#### 11.2.1.2 Accuracy by Reader

To describe the accuracy of WSI relative to Glass by reader, the MMRM logistic model (1) with the omission of reader and site variables will be used. The analyses will be the same as those for accuracy by site.

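### Protocol 9.4.2.2 draws the reader and site forest plots from a model with one common modality effect, so overlap of those intervals cannot support generalizability

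*Protocol*

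**What the plan says.** Protocol 9.4.2 defines the primary model with modality "as a fixed effect; and site, reader and case entered into the model as random effects". SAP 11.1.2 repeats this (modality "will be included in the model as fixed effect; and, site, reader, and case will be included as random effects") and writes it out as model (1): an intercept, one modality effect, and random intercepts for site, reader within site and case within site. Neither document gives modality an interaction with reader or site.

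Protocol 9.4.2.2 takes the 16 by-reader differences from this model: the difference and "associated 95% CI by reader will be constructed using the primary MMRM logistic regression model". For sites, "Generalizability for sites will be addressed in a similar way to that previously discussed for readers within sites". On interpretation it says "The extent to which the respective confidence intervals in the Forest Plot are overlapping sheds light on their homogeneity", and that "reasonably homogeneous confidence intervals can support generalizability with respect to readers".

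The SAP handles the same quantities differently. For sites (11.2.1.1), "the MMRM logistic model (1) with the omission of the site variable will be used", with rates, difference and 95% CIs reported for each of the four sites. For readers (11.2.1.2), "the MMRM logistic model (1) with the omission of reader and site variables will be used", with the same outputs. Observed rates are cross-tabulated in both. The SAP has no forest plots and no statement on generalizability.

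**The concern.** The forest plots are meant to show whether the WSI effect is similar across readers and sites. A model that already assumes one modality effect cannot answer that, because it draws similar differences even when the readers' own data disagree. A reader of the report could then take overlapping intervals as support for generalizability when the overlap comes from the model.

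The two documents also appear to prescribe different models for the same by-reader and by-site differences. The statistician must choose between them, and on the Protocol's choice the plot is uninformative.

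**Working it through.** No figure stated in the plan bears on this point. The check is algebra on model (1), a hand calculation and a simulation.

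**1. What model (1) allows.** For any case h, reader f and site l:

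logit P(WSI) − logit P(Glass) = α_WSI − α_Glass = θ

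The site, reader and case terms cancel, so θ is the same for every reader and site. On the risk-difference scale, to first order, d_f ≈ θ · p_f(1 − p_f), where p_f is the reader's overall rate. All d_f therefore have the sign of θ and differ only through p_f. Each interval is the interval for θ rescaled.

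**2. Hand example (assumed rates).** There are 16 readers with 500 cases each. Fifteen have 5% major discordance on both modalities; one has 5% on Glass and 13% on WSI. Fit one modality effect with 16 reader intercepts. The fit preserves each reader's mean rate (0.05 for fifteen, 0.09 for one) and the sum of the WSI rates:

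- 15(0.05 + d₁/2) + (0.09 + d₂/2) = 15 × 0.05 + 0.13 = 0.88, so 7.5 d₁ + 0.5 d₂ = 0.04
- d₁ = θ × 0.05 × 0.95 = 0.0475 θ; d₂ = θ × 0.09 × 0.91 = 0.0819 θ
- θ = 0.04 / (0.35625 + 0.04095) = 0.1007; odds ratio = exp(0.1007) = 1.106
- d₁ = 0.0048 and d₂ = 0.0082

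A direct numerical fit gives the same values. An observed 8 points against 0 is displayed as 0.8 against 0.5. This simplified fit has no case effect, so step 3 uses model (1) itself.

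**3. Simulation with model (1).** The layout is 4 sites × 4 readers × 500 cases × 2 modalities. Assumed: Glass rate about 3.7%; logit-scale SDs of 2.0 (case), 0.3 (reader) and 0.2 (site); one data set per scenario. Model (1) was fitted by Laplace-approximated maximum likelihood with delta-method CIs. The comparison is each reader's own paired difference with its 95% CI. There are 16 × 15/2 = 120 reader pairs. Site values are means over that site's four readers.

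| Scenario | Observed difference (points) | Model (1) difference (points) | Non-overlapping pairs: model (1) / reader-specific |
|---|---|---|---|
| A. No heterogeneity | readers −2.0 to +1.8 | +0.22 to +0.32 | 0 / 0 |
| B. One reader worse on WSI | that reader +9.6; others −2.0 to +1.8 | that reader +1.34 (0.16 to 2.52); others +0.79 to +1.28 | 0 / 15 |
| C. One site worse on WSI | sites +4.25, −0.40, +0.20, +0.40 | 1.81, 1.74, 1.57, 1.57 | 0 / 22 |
| D. Opposite effects at two sites | +3.6 and −3.0 | +0.49 and +0.45 | 0 / 32 |

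Model (1) gives complete overlap in all four scenarios. Its intervals are also narrower than one reader's data support: in B the half-widths are about 0.7 to 1.2 points, against 1.7 to 2.9 for the reader-specific intervals, because each borrows the precision of the pooled θ. Adding a modality-by-reader term in B recovers the deviant reader at +11.1 (7.7 to 14.5), with the others at −2.0 to +2.4.

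**4. What the SAP wording implies.** Within one site the site term is constant. Within one reader both the site and the reader term are constant. These are exactly the terms that SAP 11.2.1.1 and 11.2.1.2 drop, which points to separate fits. Only the organ section (11.2.1.3) says outright that the model is applied to each subgroup.

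**The case against.** The strongest reply is that the SAP already does the right thing. Version 2.0 is dated 01 AUG 2021, after Protocol Rev 4.0 of July 9, 2020, and Protocol 9.4 describes itself as a summary of what the SAP details. Separate fits are the natural reading of 11.2.1.1 and 11.2.1.2. This largely stands. A reader might infer that a pooled fit is meant, which could give no site- or reader-specific estimate, but the SAP promises estimates for each of the four sites. What remains is that the SAP does not state separate fits and does not replace the plots or their interpretation, so the Protocol's instruction still governs them.

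A reader might also infer that a poorly performing reader or site would be hidden. The documents do not support that:

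- The SAP cross-tabulates observed rates by site and by reader.
- SAP 11.1.2 lists reads that are major-discordant on one modality only, with reader ID and site.
- Protocol 9.4.3 gives differences with CIs by site, and WSI-Glass agreement with CIs for each reader.

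The example reader at 5% and 13% would be visible there. These outputs limit the harm but do not correct the forest plots.

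Finally, the plots are descriptive and no decision rule is attached to overlap. That stands, so a formal heterogeneity statistic, or a between-site variance estimated from four sites, would be a preference and is not requested. The Protocol's revision history says that interaction terms were removed in line with FDA instructions; nothing here asks for them back in the primary model.

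**Conclusion.** The point holds for Protocol 9.4.2.2 as written. The common odds ratio follows from the model's form and needs no assumption about rates. The sizes (0.8 against 0.5 point for an observed 8 against 0; 0 non-overlapping pairs where reader-specific intervals give 15 to 32 in scenarios B to D) depend on the assumed rates, variances and effects, and on one simulated data set per scenario.

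It would be too strong to say that the intervals look identical whatever the data show: on the risk-difference scale they still move with each reader's or site's baseline rate. Nor does the point touch the non-inferiority conclusion, which rests on the overall difference. The defect is a misleading descriptive display and a conflict between Protocol 9.4.2.2 and SAP 11.2.1.1 and 11.2.1.2. It should be corrected before the analysis is run.

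**What to change.** - **Protocol 9.4.2.2:** replace the reference to the primary model with separate fits, one within each site (modality fixed; reader and case random) and one within each reader (modality fixed; case random).
- **Fallback:** where a fit does not converge, use the observed paired WSI-minus-Glass difference with a 95% CI, clustered by case for sites. At the assumed 3.7% rate a single reader contributes only about 500 × 2 × 0.037 = 37 events, so the fallback should be specified in advance.
- **SAP 11.2.1.1 and 11.2.1.2:** state the same separate fits and fallback explicitly, and say that these estimates and CIs are the ones shown in the forest plots.

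The cost is wording in both documents, 4 + 16 = 20 model runs, and wider reader-level intervals that reflect what one reader's data can show. The primary model, margin and sample size do not change.

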- For resection cases, the EP shall select the set of slides that are necessary to indicate the primary diagnosis, inclusive of the key CAP checklist abridged metrics of cancer type, grade, margins and if metastasized to lymph nodes.
  - If there are multiple levels, the EP may select only the level of the same block slide that is germane to the primary diagnosis.
  - To minimize selection bias, the EP shall choose the first available H&E slide that describes that condition(s), rather than the best slide.
  - A minimum of 5 H&E slides will be selected. If the set of slides selected to define the primary diagnosis is < 5, then the EP shall continue to pick H&E slides until a minimum of 5 is achieved, and thereby the EP may pick further primary diagnosis slides, secondary diagnoses slides or slides irrelevant to any recorded diagnosis, whichever comes first.

In addition, for any case where there are extra slides with special and/or immunochemical stains, the EP shall enroll all those, as long as these extra stains are used for making/confirming the diagnosis and not for prognosis or to guide treatment (e.g. human epidermal growth factor receptor 2 [HER2] stain in breast cancer).

For enrolled slides, the EP shall remove all markings from the coverslip. If not possible, the slide shall be excluded, and another slide must be chosen.

*A priori* defined slide and case data rejection criteria have been developed per the defined inclusion and exclusion criteria in section 6. Some case data may be spurious or artifactual and may need to be disregarded, or slides may be damaged, aged, or lost, or there may be corrupted digital files, etc.

For every case enrolled, the EP shall make a determination if this case can be considered to be a “difficult and challenging” case. The EP will select “difficult and challenging” when one or more of the following apply:

- It’s professional opinion of EP that case is “difficult and challenging”
- Case used special stains or immunohistochemical stains to aid in diagnosis
- Case used molecular tests to aid in diagnosis
- Case used tumor boards to review case to aid in diagnosis
- Other reason, and brief narrative to elaborate.

The EP shall capture this information for every one of the 500 enrolled cases for that site.

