#### **11.2 Secondary Objectives Analyses**

The AAP will be used for all secondary analyses. All secondary analyses will be descriptive in nature with no hypothesis testing. Missing reads and deferred reads will be excluded from these analyses.

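### Protocol 9.4.2.2 reads reader and site homogeneity from how far confidence intervals overlap, with no measure of heterogeneity, and takes the reader intervals from a model that cannot show reader differences in the modality effect

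*Protocol*

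**What the plan says.** Protocol 9.4.2.2 is the only generalizability analysis in either document. On readers it states: "The 16 such confidence intervals for the 4 readers at the 4 sites will be descriptively displayed in a Forest Plot". On how to read the plot: "The extent to which the respective confidence intervals in the Forest Plot are overlapping sheds light on their homogeneity". It adds that reasonably homogeneous intervals can support generalizability, in the sense that the estimated differences are comparable across the study's readers. The same reading is repeated for the 4 site intervals. There is no cut-off, no pass/fail criterion, no heterogeneity statistic and no estimate of how much the WSI–Glass difference varies between readers.

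The two documents differ on where the reader intervals come from:

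- Protocol 9.4.2.2: "95% CI by reader will be constructed using the primary MMRM logistic regression model". Protocol 9.4.2 describes that model as modality fixed, with "site, reader and case entered into the model as random effects". SAP 11.1.2 writes the same terms as model (1). Neither has a reader-by-modality or site-by-modality term.
- SAP 11.2.1.2: "the MMRM logistic model (1) with the omission of reader and site variables will be used". SAP 11.2.1.1 drops the site term for the by-site results.

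The SAP has no forest plot and no generalizability section. Of these analyses SAP 11.2 says: "All secondary analyses will be descriptive in nature with no hypothesis testing".

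**The concern.** The plan draws a conclusion, that the result generalizes over readers and sites, from a visual impression whose error properties nobody has stated. Overlap of separate 95% intervals is not a test of equality and not an estimate of spread. For a single pair it is very conservative. Over 16 readers there are 16 × 15 / 2 = 120 pairs, so some non-overlap by chance becomes common. With no rule, two people can look at the same plot and reach opposite conclusions.

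The model adds a second problem. If all readers share one modality effect by construction, the plot shows agreement because the model imposed it.

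At stake is the generalizability statement only. No margin, endpoint or primary decision depends on it.

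**Working it through.** **Inputs from the documents.** 16 readers, 4 per site, all four at a site reading the same cases (Protocol 8.7). About 500 cases per reader: "The EP shall capture this information for every one of the 500 enrolled cases for that site" (Protocol 8.3; Protocol 6.2 allows 400 to 600 per site; SAP model (1) indexes cases only to 250, and 500 is used here). Margin 4 points. λ, the correlation between the two modalities for the same reader, at least 0.5; ξ−η at most 0.15 (Protocol 9.2). WSI discordance ceiling 7% (Protocol 9.4.2).

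**Assumptions not in the documents.** True major discordance rates of 3% to 7%, and equal precision across readers.

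**Step 1. Reproduce the plan's own figures.** n = (1.960 + 1.282)² σ² / (δ + Δ)², with σ² = [π'W(1−π'W) + π'G(1−π'G)] × {1 − λ + 3(ξ−η)} / 4. Summing the two binomial variances is what reproduces Table 4. At agreement 0.6, λ = 0.5, ξ−η = 0.15:

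- Δ = 0: σ² = 0.48 × 0.95 / 4 = 0.114, n = 748.7 (Table 4: 749).
- Δ = −1.5%: n = 1903.7 (Table 4: 1904).

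The documents give no error rate for the overlap reading, so there is nothing further to match.

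**Step 2. Intervals from the primary model.** With one shared log odds ratio b, reader r's difference is expit(a_r + b) − expit(a_r), about b × p_r(1 − p_r). Readers can differ only through their baseline rate. An approximate simulation used SE(b) = √[2p(1−p) × 0.95 / (4 × 2000)] / [p(1−p)], which is 0.071 at p = 5%. Identical readers produced a non-overlapping pair in less than 0.01% of trials. With one reader truly 4 points off, all 16 intervals still overlapped in over 99.9% of trials at rates of 3%, 5% and 7%.

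**Step 3. Separate estimates, no true heterogeneity.** Two equal-width 95% intervals miss each other when the estimates differ by more than 2 × 1.96 = 3.92 SE.

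- One pair: P(|Z| > 3.92/√2) = 0.56%.
- Any of 120 pairs, independent readers: upper tail of the range of 16 standard normals at 3.92 = 28.5%, whatever the SE. With sites of 400 to 600 cases it is 28.7%.
- Readers at a site share cases. The correlation of two readers' differences is (ξ−η)/(1−λ) = 0.15/0.5 = 0.30 at the plan's bound, and the figure falls to 23%.
- The 4 sites (range of 4 normals): 2.9%.

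**Step 4. Separate estimates, two pre-named readers at different sites, truly 4 points apart.** SE = √[2p(1−p)(1−λ)/500]. P(overlap) is the probability that the two estimates differ by at most 3.92 SE, when their difference has mean 4 points and SD √2 × SE. With λ = 0.5:

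| Discordance rate | SE (points) | 3.92 SE (points) | P(overlap) |
|---|---|---|---|
| 3% | 0.76 | 2.99 | 17% |
| 5% | 0.97 | 3.82 | 45% |
| 7% | 1.14 | 4.47 | 61% |
| 20% to 40% (Table 4 agreement 0.8 to 0.6) | 1.79 to 2.19 | 7.01 to 8.59 | 88% to 93% |

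**Step 5. Same 4-point gap, one reader against the other 15, any-pair reading.** At the 5% settings a non-overlapping pair appears in about 96% of trials. A binary-data simulation with λ of about 0.32 to 0.38 gives 77% (7% rate) to 93% (3% rate).

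**Step 6. A calibrated alternative at the 5% settings.** Cochran's Q on 15 df exceeds its 5% critical value in 5.0% of trials with identical readers. It does so in 67% at a between-reader SD of 1 point and 94% at 1.5 points. With within-site correlation 0.30 the figures are just under 5%, 63% and 94%.

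**The case against.** The strongest reply is that the Protocol sets no rule at all. The plot is descriptive, the wording is about extent, and homogeneous intervals are said only to be able to support generalizability. That stands. A reader might infer that the plan contains a criterion with a 29% false-alarm rate. It does not: 29% belongs to an any-pair reading that the text permits but does not prescribe, it assumes independent readers, and it does not apply to intervals taken from the primary model.

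A reader might also infer that the display would often hide a reader who is off by the full margin. With separate estimates that holds only for a pre-named pair, and only at some rates: under half of trials at 5%, rare at 3%. Looking over all 16 intervals, one such reader is usually flagged (Step 5).

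Two further points stand. The Protocol confines its meaning of generalizability to comparability across the study's own readers and sites, so it should not be read as a claim about pathologists at large. And the SAP, which Protocol 9.4 names as the detailed source, treats these results as descriptive, so a formal test would cut against that choice. For the 4 sites the any-pair false alarm is only about 3%, so calibration is mainly a reader problem.

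What the reply does not answer is that a conclusion is still drawn from the plot with no quantity behind it. Under the Protocol's own wording the reader intervals are close to uninformative about what they are meant to show.

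**Conclusion.** The point holds as a minor weakness of method. Overlap is a poor gauge of homogeneity, and how it fails depends on which document's model is used. From the primary model, overlap is almost guaranteed. From separate reader estimates, any non-overlapping pair would be seen in about 23% (within-site correlation 0.30) to 29% (independent) of trials with identical readers, so such a flag is hard to interpret.

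The pairwise figures rest on assumed discordance rates, λ = 0.5, 500 cases per reader and equal precision. The Step 2 result rests on an approximate simulation, but its direction follows from the absence of a reader-by-modality term. The documents do not support the inference that the non-inferiority conclusion is at risk: the primary test does not use this display.

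**What to change.** 1. Keep both forest plots, but estimate the WSI–Glass difference separately for each reader and each site. SAP 11.2.1.2 already fits this if read as one model per reader. Say so explicitly there, and bring Protocol 9.4.2.2 into line, since it now points to the primary model.
2. Replace the overlap sentences in Protocol 9.4.2.2 with a report of the between-reader SD of the difference and its 95% CI. Give Cochran's Q alongside (15 df for readers, 3 df for sites) as a descriptive statistic, with no pass/fail threshold, in keeping with SAP 11.2.
3. Add a matching short paragraph to the SAP, which has no generalizability section at present. Note there that readers within a site share cases.

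The cost is about one paragraph in each document and a few lines of program code. No new data are needed, and the primary analysis does not change.
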